- the decision of the OHGPS phone operator.
- all data on the intervention form for both study arms, for each patient, who gave IC. These data consist of those filled in by the GP on-call immediately after the intervention (Table 2)
 - o first (when deciding on referral) and final (when completing the intervention form) diagnostic hypothesis;
 - o referral to hospital or not;
 - o parameters and curves inspected and results;
 - o if any alarm was given and noticed;
 - o the impact of the device parameters on the decision;
 - o if the device brought new elements;
 - o the feeling of the GP about the improvement or not by the device in communication with the healthcare professional;
 - o which parameters helped the communication and if they were showed or viewed by the EP.
- After 30 days
 - o the information provided by the patient's own regular GP, regarding the patient's outcome;
 - o the information concerning the diagnosis at arrival at the ED and, if available, the outcome of the patient until day 30 of the hospital admission.

Analysis

I will compare the amount of (verified or experienced) emergencies with the non-urgent home visits, the number of patients correctly referred to hospital or not. The difference in proportions in both groups will be tested by the Z-test. I will also test for the difference in proportions in the groups using the monitoring device and the usual care group, with the z-statistic for two-sample test of proportions reporting the z-test statistic and the associated *p*-values. All *p*-values smaller than 0.05 will be considered statistically significant. The statistical analyses will be performed with R software version 3.5.1 [20].

The definition of an incorrect referral is stated as follows:

- When a patient is referred to hospital and released within 12 hours. However, if the referral is made only for a diagnostic test, e.g. an X-Ray, an ECG, a blood test, advice of a consultant .., and no hospitalisation followed, it is considered as a correct referral.
- If a patient is referred to hospital only for a diagnostic test (e.g. X-Ray) and no hospitalisation is requested, but an in-hospital decision is made to hospitalise the patient.
- If a patient is referred to his own GP but needs a hospitalisation within 48 hours.

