The alarms are produced by the device when a wire is not registering or is disconnected, when the battery is low, when apnoea or asystole is present, or when the value is out of the set limits for each parameter. Therefore, alarms will be enabled on each device and the upper and lower limits will be set on each device. I will use the device's pre-installed lower limits: for SpO₂ ≤92%, for respiration rate (RR) at ≤10 respirations per minute and the upper limits for temperature at ≥39°C and for HR at ≥120 beats per minute (bpm). I will change the automatically set lower limits for pulse rate and HR at ≤50 bpm instead of 30 bpm and the upper limit for RR to ≥30 respirations per minute.

Referral

The data produced by the device could help the GP to follow the evolution of the disease and to establish his tentative diagnosis. Deciding about the treatment and referral of the patient to hospital or to their own GP, is the responsibility of the GP and is based on his usual approach of the situation.

It was needed to decide what a correct referral is. A referral to the patient's own GP is considered incorrect if the patient cannot be treated at home up to 48 hours after the initial urgent visit and has to be admitted to hospital. It is however considered as correct if the patient needs to be hospitalised for another reason than the reason of the home visit. In exceptional cases, the patient could request a new urgent visit during the same out-of-hours period. The visiting GP will include the patient if the informed consent is obtained and follow the study procedure, but will record that the patient was seen less than 48 hours before. The first home visit referral is consequently considered as incorrect. It is also possible that a patient is transported by ambulance or MET within 48 hours of the GP on-call visit: the referral will then be considered as incorrect if the patient was initially sent home, based on the records obtained from the patient's own regular GP, 30 days after the first intervention.

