For hospitalised patient the discussion about correct referrals leads to important decisions. The threshold is set at 12 hours. When a patient is referred to hospital for admission and he stays more than 12 hours in hospital (at the ED), it is considered a correct referral. A correct referral is when the patient is referred only for an investigation, e.g. a X-Ray or an ECG or a blood test, and was not hospitalised. If the referral for an investigation leads to admission to hospital, it is considered as an incorrect referral, as well as if a hospitalisation is requested and the patient leaves the hospital within 12 hours.

Parameters and communication

I currently could not find literature concerning the accuracy of the communication between GPs and EPs. However, it is described in the literature that the communication in-between emergency professionals at any level was not optimal and could certainly be improved [12]. They tend to focus on diagnosis and give incomplete information on parameters or signs and symptoms [13,26]. In this trial, the aim is also to assess whether the GPs' communication with the EPs is better when the monitor is used than when it is not used. Moreover, the objective is also to know which of the parameters is used as an additional argument in the communication, either orally, either by showing the parameter(s) on the device, or by recording the parameter(s) in the referral letter.

Comments of the GPs on-call

On the intervention form, GPs are asked to record elements regarding communication, user-friendliness of the device and general comments. All answers will be coded by two investigators separately and, in case of disagreement, after agreement between both or after consulting a third person.

Based on the results, general conclusions can be drawn for improvement of the device and for future research.

Outcome after 30 days

A letter will be sent to the regular GPs of the included patients 30 days after the GP-on-call intervention, to know if the patients stayed at home more than 48 hours and what the evolution was until day 30: cured, relapse, needed hospitalisation after more than 48 hours for the same reason or not, patient was not seen again or was not a patient of the practice. I also will check whether the GP received a discharge letter of the hospitalised patient. That information aims to evaluate the correct or incorrect nature of the referral by the visiting GP on-call.

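### The referral endpoint judges hospital need by inconsistent criteria for referred and left-at-home patients, so some short-stay patients are scored incorrect under either decision

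*Combined protocol and SAP*

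**What the plan says.** The rules stand in two places: the list defining an incorrect referral (Statistics, Analysis), and the Referral section of the Discussion.

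**Referred patients.** The first item in the Analysis list is "When a patient is referred to hospital and released within 12 hours". An exemption follows: "However, if the referral is made only for a diagnostic test, e.g. an X-Ray, an ECG, a blood test, advice of a consultant", provided that no hospitalisation follows. The second item makes a test-only referral incorrect if the hospital then decides to admit. The Discussion agrees. If the patient was referred for admission and "he stays more than 12 hours in hospital (at the ED), it is considered a correct referral"; a referral is incorrect if a test leads to admission, "as well as if a hospitalisation is requested and the patient leaves the hospital within 12 hours".

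**Patients left at home.** The third Analysis item is "If a patient is referred to his own GP but needs a hospitalisation within 48 hours". The Discussion first words this as a patient who "cannot be treated at home up to 48 hours after the initial urgent visit and has to be admitted to hospital", and excuses admission for an unrelated reason. It then adds two triggers that the Analysis list lacks. A repeat urgent visit in the same out-of-hours period makes the first decision incorrect. And: "It is also possible that a patient is transported by ambulance or MET within 48 hours of the GP on-call visit", in which case "the referral will then be considered as incorrect if the patient was initially sent home".

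Neither section defines hospitalisation for scoring, and neither sets a minimum stay for a patient left at home.

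**The concern.** The proportion of correct decisions is the outcome behind the first study aim, the sample size and the z-test. It should show whether the GP's decision fitted the patient's need for hospital. Here the evidence of need depends on the decision. A referred patient shows need by staying more than 12 hours. A patient left at home can show it by an ambulance journey or a second visit, however short any hospital contact turns out to be.

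Where the two sets of rules overlap, a patient is an error under both decisions. No device can remove such errors, so they shrink the difference that the trial can show. Because the two sections differ on transport and repeat visits, two reviewers could also score the same patient differently, each with support in the text.

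**Working it through.** **Step 1: score one kind of patient by each route.** Take a patient whose hospital need is a few hours of ED treatment.

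| Decision and course | Analysis list | Discussion, Referral |
|---|---|---|
| Referred for more than a test or advice, released within 12 h | Incorrect | Incorrect where hospitalisation was requested |
| Referred for a test or advice only, not hospitalised | Correct | Correct (the examples are all investigations) |
| Left at home, settles | Correct | Correct |
| Left at home, reaches the ED by own means, treated, not admitted | Correct on the literal wording | Correct on the literal wording |
| Left at home, briefly admitted within 48 h for the same reason | Incorrect | Incorrect |
| Left at home, ambulance or MET within 48 h, released without admission | Not listed as incorrect | Incorrect |
| Left at home, repeat urgent visit in the same period | Not listed as incorrect | Incorrect |

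The first row combined with any of the last three gives an incorrect score under both decisions. Brief admission does so under both sections; transport and repeat visit do so only under the Discussion.

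**Step 2: the planned effect.** Inputs from the Sample size section: 21% inappropriate decisions, an 11% gain, 433 per arm. Inputs from the Analysis section: z-test for two proportions, significance at 0.05. Assumptions: the 11% is absolute (21% to 10% incorrect) and the test is two-sided. The planned share of errors removed is 11/21 = 52%.

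Power is not stated, so 433 cannot be reproduced from the stated inputs. With 21% against 10%, the pooled-variance z-test needs 169 per arm for 80% power and 226 for 90%. At 433 per arm, power is 99.4%. That is a separate matter, but it sets the reserve against which dilution should be judged.

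**Step 3: the effect of a floor.** Let q be the share of all patients scored incorrect either way. It is assumed, because the documents give no figure, and is taken as part of the 21%. The device removes 11/21 of the other errors, so:

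- p1 = 0.21 and p2 = q + (0.21 − q) × 10/21
- z = [ (p1 − p2) − 1.96 × √(2p̄(1 − p̄)/433) ] / √( [p1(1 − p1) + p2(1 − p2)]/433 ), where p̄ = (p1 + p2)/2
- power = Φ(z)

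For q = 0.05: p2 = 0.05 + 0.16 × 10/21 = 0.1262, the difference is 0.0838, and z = (0.0838 − 1.96 × 0.0254)/0.02525 = 1.35, so power is 91.1%.

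| q (points of the 21) | p2 | Difference (points) | Power at 433 per arm |
|---|---|---|---|
| 0 | 10.0% | 11.0 | 99.4% |
| 2 | 11.05% | 9.95 | 98.0% |
| 5 | 12.6% | 8.4 | 91.1% |
| 8 | 14.2% | 6.8 | 75.0% |

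**Step 4: a milder assumption.** Suppose instead that the 21% and 10% describe only the other patients, with the floor on top. At q = 8 points the rates are 0.08 + 0.92 × 0.21 = 27.3% and 0.08 + 0.92 × 0.10 = 17.2%, a difference of 10.1 points with power 94.9%. At q = 5 points, power is 97.3%.

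**The case against.** **The rule is deliberate.** The Discussion openly sets and explains the 12-hour threshold. Needless referral and missed admission are different errors, so different markers are not a fault in themselves. That stands, and it is a reason to keep the rule as primary. It does not explain why the transport and repeat-visit triggers carry no admission condition when the Analysis list requires hospitalisation.

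**The transport sentence may only illustrate the admission rule** that it follows. This reading is possible, but the sentence does not say so. The ambiguity itself needs resolving.

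**Not every short-stay patient is caught.** A reader might infer that no decision about such a patient can ever be scored correct. The text does not support this. A patient left at home who settles, or who reaches the ED by own means and is not admitted, is correct on the literal wording, as is a referral made only for a test or advice.

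**Effect on the device.** A reader might infer that the heart-rate and SpO₂ alarms steer GPs towards patients who are treated and sent home, and that these referrals count against the device. The documents give alarm limits, not what becomes of patients who trigger them. Nor does a referral cost the device anything for a patient who would be incorrect either way. A change in how often GPs refer could move the score for other short-stay patients, but its direction and size are unknown.

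**Power is ample.** This stands for a small floor. Power falls below 80% only when q is near 8 of the 21 points, which would be a large share for so narrow a group.

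**Conclusion.** The inconsistency is real and should be corrected before outcomes are scored. The Analysis list and the Referral section disagree on when a patient left at home counts as an error. Read together, they score some short-stay patients incorrect whichever way the GP decides.

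The consequence is dilution and uncertain scoring. It is not automatic bias between arms, because both arms are scored by the same rules. If the floor lies within the 21%, power at 433 per arm falls from about 99% to 98%, 91% or 75% for floors of 2, 5 or 8 points; if it comes on top, the loss is smaller. These figures rest on an assumed share, the absolute reading of 11%, a two-sided test, and a device that removes 52% of the remaining errors.

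A reader might go further and conclude that any ED treatment should replace the 12-hour rule as the primary criterion. The documents do not support that. Minor treatment could then count as hospital need, and the rules on test-only referrals and repeat visits would still be unreconciled.

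**What to change.** These changes concern endpoint scoring only, not whom to refer.

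1. Reconcile the Analysis list with the Referral section in one set of scoring rules, and define hospitalisation once for both decisions.
2. Apply to late ambulance or MET transports and to repeat visits the same admission and 12-hour condition as to initial referrals. Take length of stay from the ED health-record check announced in the Abstract.
3. Keep the 12-hour rule as primary. Prespecify a sensitivity analysis in which patients referred, treated in the ED and released within 12 hours are scored correct, with the same criterion of need applied to patients left at home.
4. State how both analyses handle a test-only referral that ends in admission, which the second Analysis item now scores as incorrect.

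**Cost.** The Appendix data sheet has no field for purpose of referral or length of stay. Both must be added, with a yes/no item for ED treatment and a short definition for the reviewers. The ED record must also be checked for patients left at home and later transported. The Referral section scores them from the regular GP's records, and the hospital follow-up under Outcome after 30 days is described for hospitalised patients. This is modest extra record review, with no change to recruitment or sample size.

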The study will last for six months, depending on the number of recruited patients with a minimum of 866 cases where an ICF is obtained or when article 29 and 30 of the WMA Declaration of Helsinki is applicable.

Quality assurance

The device, InnoCare PICO™, Type IMH-8M is a portable colour patient monitor and developed, manufactured and distributed by Innomed Medical Inc., *Medical Developing and Manufacturing Inc.*, [name], [contact], [contact], <http://www.innomed.hu>, and labelled CE 0120.

Ethics and regulatory approvals

The study was approved by the ethical committee of KU Leuven under the S-number S63046 on 2020, October 07.

DISCUSSION

Feasibility of the study

In order to be able to design the study, it was necessary to know whether sufficient acute cases could be included for this study. To do so, we first contacted the responsible persons and requested the number of urgent calls and home visits. Based on their figures about the number of home visits, it seems feasible to start the study. As explained, both emergency numbers arrive at the central dispatch. Consequently it is possible that less urgent cases will reach the OHGPS because the 112 dispatcher

assumes that a specific call coming from 1733 needs immediate intervention by the MET, PIT or ambulance. Future studies should examine the distribution of calls and compare the decision to the outcome.

Introducing the study and the monitoring device

GPs regularly see urgent cases at home during their out-of-hours service and carry their usual doctor's bag with them. For this study, however, they will be burdened with extra tasks, namely the introduction of the monitoring device. Therefore, it is needed to clarify the following points: how to introduce the monitoring device into the routine of the GPs, how can the use of the PICO™ be explained to the GPs and chauffeurs, who will apply it onsite, what are the requirements to be able to apply this device?

To introduce the study and the monitor, we need an agreement of the people in charge of the OHGPS. Two meetings will be organised, one for the GPs and one for the chauffeurs, to explain the design of the study and how the process will be developed. These meetings have not taken place yet due to the current pandemic (see below).

To explain how to use and apply the PICO™, a written manual and an extensive video have already been prepared. Each participant will receive a written copy and access to the training video at all time.

Since in case of urgency GPs must be able to focus on the patient, we decided that the chauffeur would accompany the GP to the patient and connect the device if asked to do so according to the randomization process. One of the reasons is that the turn-over of the chauffeurs is lower than of the GPs on call, which means that the risk of errors due to incorrect application or protocol violations will also be lower.

Urgent home visits

Each time a patient asks a doctor for a home visit during out-of-hours periods, it is considered as an urgent call. For a non-urgent problem, the patient is considered to be able to visit the OHGPS, where a physician can be consulted. Therefore, it was considered feasible to perform randomisation before the patient was seen.

Randomisation

For this randomised control trial, the number of cases needed is first calculated. Each case is allocated to the result of the randomisation. The monitoring device will be installed accordingly. It was decided to stratify at the OHGPS level and by the intervention vehicle. For each vehicle, the block randomisation will be applied in blocks of six. Each intervention form will be used according to the assigned rank number for which an envelope with the result of the randomization is provided. Block randomisation

was chosen because sometimes two vehicles and GPs are on the road at the same time and home visits can therefore be executed simultaneously.

Consequently, at the start and certainly before the GP leaves the vehicle, the randomisation envelope will be opened to know if for that specific home visit the monitoring device will be used. If the decision is to apply the monitoring device, the chauffeur has to accompany the GP. In the other situation, he will not and the GP will provide care as per usual.

In the intervention arm, the monitoring device will be applied, with one pulse oximeter device on a finger and five electrodes on the bare chest of the patient for an ECG. If needed, the GP can also apply the thermometer. When another investigation is done simultaneously, e.g. a full ECG record by another device, this will be considered as usual care and mentioned in the intervention form.

Informed consent form and patient's agreement

At each home visit an informed consent must be obtained, as required by Belgian law and at the request of the ethics committee. The patient is given a short explanation orally, after which the patient can give his oral consent, which must be noted on the intervention form. The ICF, drawn up in duplicate, must be signed by the patient or his legal representative and by the GP.

In a very urgent situation, obtaining informed consent will be difficult, such as with a very seriously ill patient or if he or she is alone. There is then either hardly time to provide much explanation or the patient can hardly or no longer understand. The explanation should be very short: the GP should ask the patient if he agrees that the home visit may be part of a study and that it will not affect his health status in any way. If the device has to be installed, it will also be stated that it is only installed non-invasively.

In order not to lose important information, it is decided that in these cases, after the intervention, one should try to contact the patient or his legal representative. If this is not possible, the obtained data must be excluded from the study. Although, based on the WMA declaration of Helsinki, the data of some patients can still be used. This is also stated in the ICF. The declaration states that research involving subjects who are physically or mentally incapable of giving consent, for example, unconscious patients, may be done only if the physical or mental condition that prevents giving informed consent is a necessary characteristic of the research population. If no legally authorized representative is available and if the research cannot be delayed, the study may proceed without informed consent provided that the specific reasons for involving subjects with a condition that renders them unable to give informed consent have been stated in the research protocol (see study design) and the study has been approved by a research ethics committee (see below).

It is up to the researchers to check whether these conditions have been met and whether the GP has written down on the intervention form the reason for not obtaining the informed consent and the diagnosis.

Alarms of the monitoring device

The alarms are produced by the device when a wire is not registering or is disconnected, when the battery is low, when apnoea or asystole is present, or when the value is out of the set limits for each parameter. Therefore, alarms will be enabled on each device and the upper and lower limits will be set on each device. I will use the device's pre-installed lower limits: for SpO₂ ≤92%, for respiration rate (RR) at ≤10 respirations per minute and the upper limits for temperature at ≥39°C and for HR at ≥120 beats per minute (bpm). I will change the automatically set lower limits for pulse rate and HR at ≤50 bpm instead of 30 bpm and the upper limit for RR to ≥30 respirations per minute.

Referral

The data produced by the device could help the GP to follow the evolution of the disease and to establish his tentative diagnosis. Deciding about the treatment and referral of the patient to hospital or to their own GP, is the responsibility of the GP and is based on his usual approach of the situation.

It was needed to decide what a correct referral is. A referral to the patient's own GP is considered incorrect if the patient cannot be treated at home up to 48 hours after the initial urgent visit and has to be admitted to hospital. It is however considered as correct if the patient needs to be hospitalised for another reason than the reason of the home visit. In exceptional cases, the patient could request a new urgent visit during the same out-of-hours period. The visiting GP will include the patient if the informed consent is obtained and follow the study procedure, but will record that the patient was seen less than 48 hours before. The first home visit referral is consequently considered as incorrect. It is also possible that a patient is transported by ambulance or MET within 48 hours of the GP on-call visit: the referral will then be considered as incorrect if the patient was initially sent home, based on the records obtained from the patient's own regular GP, 30 days after the first intervention.

For hospitalised patient the discussion about correct referrals leads to important decisions. The threshold is set at 12 hours. When a patient is referred to hospital for admission and he stays more than 12 hours in hospital (at the ED), it is considered a correct referral. A correct referral is when the patient is referred only for an investigation, e.g. a X-Ray or an ECG or a blood test, and was not hospitalised. If the referral for an investigation leads to admission to hospital, it is considered as an incorrect referral, as well as if a hospitalisation is requested and the patient leaves the hospital within 12 hours.

Parameters and communication

I currently could not find literature concerning the accuracy of the communication between GPs and EPs. However, it is described in the literature that the communication in-between emergency professionals at any level was not optimal and could certainly be improved [12]. They tend to focus on diagnosis and give incomplete information on parameters or signs and symptoms [13,26]. In this trial, the aim is also to assess whether the GPs' communication with the EPs is better when the monitor is used than when it is not used. Moreover, the objective is also to know which of the parameters is used as an additional argument in the communication, either orally, either by showing the parameter(s) on the device, or by recording the parameter(s) in the referral letter.

Comments of the GPs on-call

On the intervention form, GPs are asked to record elements regarding communication, user-friendliness of the device and general comments. All answers will be coded by two investigators separately and, in case of disagreement, after agreement between both or after consulting a third person.

Based on the results, general conclusions can be drawn for improvement of the device and for future research.

Outcome after 30 days

A letter will be sent to the regular GPs of the included patients 30 days after the GP-on-call intervention, to know if the patients stayed at home more than 48 hours and what the evolution was until day 30: cured, relapse, needed hospitalisation after more than 48 hours for the same reason or not, patient was not seen again or was not a patient of the practice. I also will check whether the GP received a discharge letter of the hospitalised patient. That information aims to evaluate the correct or incorrect nature of the referral by the visiting GP on-call.

